### 7.2. Secondary Analyses

The following endpoints will be summarised in the same way as the primary endpoint (Section [7.1](#)).

- The number and percentage of subjects successfully able to self-administer their unobserved second dose at Week 4. The denominator for the percentage calculation will be the number of subjects attempting an injection at Week 4.
- The number and percentage of subjects successfully able to self-administer their observed first dose at Week 0. The denominator for the percentage calculation will be the number of subjects attempting an injection at Week 0.
- The number and percentage of subjects successfully able to self-administer both their unobserved second dose at Week 4 and their observed third dose at Week 8. The denominator for the percentage calculation will be the number of subjects attempting an injection at both Week 4 and Week 8.
- The number and percentage of subjects successfully able to self-administer all three doses at Week 0, 4 and 8. The denominator for the percentage calculation will be the number of subjects attempting all three doses at Week 0, 4 and 8.

Data collected on the observer checklist for in-clinic injections and subject completed checklists for home injections will be summarised. The investigator assessment of user/device errors will be summarised by visit. Device usability/functionality assessed by the subject at the end of the study will also be summarised.

Full details of data displays being presented in [Appendix 8: List of Data Displays](#).

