## 5.5. Withdrawal/Stopping Criteria

A subject may withdraw from study treatment at any time at his/her own request, or may be withdrawn at any time at the discretion of the investigator for safety, behavioural, or administrative reasons. If a subject withdraws from the study, he/she may request destruction of any samples taken, and the investigator must document this in the site study records. As the aim of this study is to evaluate the use of the mepolizumab liquid drug product, in autoinjector presentation, for delivery of mepolizumab, subjects who permanently withdraw from study treatment will also be withdrawn from the study (see Section 5.5.1). Reasons for premature discontinuation of study treatment will be captured in the CRF.

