## 6.8.2. Self-Administration Outside the Clinic

The subject (or caregiver) will self-administer the dose of study treatment outside the clinic and without observation during Week 4, up to 24 hours after attending clinic Visit 3. The subject/caregiver will complete a checklist of the steps required to use the autoinjector, which will also include the date and time of dose, site of injection, person administering the dose (subject/caregiver) and the ease with which the subject/caregiver was able to complete each of the critical steps required to administer the dose from the autoinjector. In addition, the subject will complete the patient diary capturing the pain experienced by the subject immediately following, 1- and 24-hours after the dose.

Subjects will be instructed to contact clinical study staff if they have concerns or questions regarding self-administration. They will have the option of returning to the clinical site for further training or assistance with self-administration. Requirement for additional training will be documented.

Compliance with the autoinjector will be assessed through reviewing the subject completed checklist, inspection of the returned autoinjector and querying the subject during the next site visit (Visit 4) and documented in the source documents.

For self-administration of mepolizumab outside of the clinic (at home), subjects should be instructed to call the investigator and/or go to an Emergency Department for any unusual symptoms (e.g. skin rash [hives] or redness, swelling of the face or mouth, becoming wheezy, coughing or having difficulty in breathing and/or feeling weak or light headed).

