#### 204959

## 7.1. Time and Events Table

		Pre-screening Week -6 to Week - 5ª	Screening Week -4 to Week - 1	Week 0 (Day 1)	Week 4 (±7 days)	Week 8 (±7 days)	Week 12 (±7 days)
		v					Early Withdrawal b
Procedures	Visit number	V0	V1	V2	V3	V4	V5
Informed consent		Х					
Demography/child bearing status asso	essment	Х					
Medical history			Х				
Asthma and Exacerbation history		Х					
Asthma Therapy history		Х					
Smoking history			Х				
Parasitic screening c			Х				
Prior needle use / self-administration	assessment		Х				
Inclusion/Exclusion criteria			Х				
Training session				Xď			
Autoinjector self-administration in clinic				Х		Х	
Autoinjector self-administration outsid	e of clinic				X e, f		
Laboratory:							
Urine pregnancy test			Х	Xď	Xď	Xď	Х
Hematology (including eosinophils) g /	Clinical Chemistry		Х	Xď	Xď	Xď	Xď
Urinalysis			Х				
Immunogenicity				Xď			Xď
PK				Xď	Xď	Xď	Xď
Pharmacogenetics h				Х			
Physical/Clinical:							
Vital signs i			Х	Xq	Xď	Xď	Х
12-lead ECG			Х				Х
Physical examination			Х				Х
Weight			Х				
Concomitant Medication		Х	Х	Х	Х	Х	Х
Asthma Exacerbations			Х	Х	Х	Х	Х
Serious Adverse Events j,k,l		Х	Х	Х	Х	Х	Х
Adverse Events j,k,l				Х	Х	Х	Х

	Pre-screening Week -6 to Week -	Screening Week -4 to Week -	Week 0 (Day 1)	Week 4 (±7 days)	Week 8 (±7 days)	Week 12 (±7 days)
	5	1	,			End of Study/ Early Withdrawal b
Procedures Visit number	VO	V1	V2	V3	V4	V5
Dispense patient diary			Xm	Х	Х	
Return/review patient diary				Х	Х	Xn
Dispense autoinjector for self-administration outside of clinic				Х		
Return/ inspect autoinjector following self-administration					Х	X n,o
outside of clinic						
Subject completed pain assessment diary (0, 1- and 24-			Х	Xf	Х	
hours post dose)						
Autoinjector observer assessment checklist			Х		Х	
Subject/caregiver completed autoinjector checklist				Xf		
Assessment of injection success			Х		Xp	
Device usability/functionality questionnaire						Х
Exit Interview Q						(X)

a. Pre-screening Visit can occur on the same day as the Screening Visit but must be completed prior to initiating any Visit 1 procedures; The Pre-screening Visit can be conducted up to a maximum of 2 weeks prior to the Screening Visit.

- b. The Early Withdrawal Visit will occur 4 weeks (±7 days) after last dose of mepolizumab for any subject who withdraws prior to Week 12

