#### 2016N275054\_04

#### CONFIDENTIAL

204959

o. Assessment to be completed at the Early Withdrawal visit only if the dose of mepolizumab immediately prior to withdrawal was administered outside of the clinic.

- p. Includes both the injection outside the clinic from Week 4 and the injection in clinic at Week 8
- q. In a subset of subjects only. Completed over the telephone after the End of Study/Early Withdrawal Visit

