#### Secondary Endpoints

The following will be summarized, including 95% CIs:-

- The number and percentage of subjects successfully able to self-administer their unobserved second dose at Week 4. The denominator for the percentage calculation will be the number of subjects attempting an injection at Week 4.
- The number and percentage of subjects successfully able to self-administer their observed first dose at Week 0. The denominator for the percentage calculation will be the number of subjects attempting an injection at Week 0.
- The number and percentage of subjects successfully able to self-administer both their unobserved second dose at Week 4 and their observed third dose at Week 8. The denominator for the percentage calculation will be the number of subjects attempting an injection at both Week 4 and Week 8.
- The number and percentage of subjects successfully able to self-administer all three doses at Week 0, 4 and 8. The denominator for the percentage calculation will be the number of subjects attempting all 3 doses at Week 0, 4 and 8.

Data collected on the observer checklist relating to the correct use of the autoinjector and any device related issues preventing the full dose being administered will be summarized at each visit.

The root cause evaluation of each unsuccessful injection via the Autoinjector (Pen) Error/Failure Reporting Form, including any observations noted by GSK Device Engineering, will be summarized separately by GSK Device Engineering for inclusion into the study report.

Device usability/functionality assessed at the end of the study will be summarized.

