[1] Blood eosinophil count immediately before starting mepolizumab that was  $\geq 150$  cells/uL or a blood eosinophil count that was  $\geq 300$  cells/uL in the 12 months prior to starting mepolizumab.

[2] Subjects currently receiving treatment with mepolizumab only.

userid: /arenv/arprod/compound/study/final/drivers/drivername.sas DDMMYYYY HH:MM

Example TAB\_POP5  
Protocol: 204959  
Population: All Subjects (Safety)

Table X  
Summary of Previous Mepolizumab Clinical Trials

		Liquid Autoinjector (N=XX)
Did the subject participate in a previous mepolizumab trial?	n	XX
	No	XX (XX%)
	Yes	XX (XX%)
Protocol number	115666	XX (XX%)
	204471	XX (XX%)
	205667	XX (XX%)

Example TAB\_INJ1  
 Protocol: 204959  
 Population: All Subjects (Safety)

Table X  
 Summary of Proportion of Subjects Successfully Able to Self-Administer Injection by Visit - First Attempt  
 Autoinjector with Standard Label + Pictogram

Visit	Liquid Autoinjector (N = XX)		
	Attempted Injections	Successful Injections [1]	
	n (%)	n (%)	95% CI
WEEK 0	XX (XX%)	XX (XX%)	(XX%, XX%)
WEEK 4	XX (XX%)	XX (XX%)	(XX%, XX%)
WEEK 8	XX (XX%)	XX (XX%)	(XX%, XX%)
WEEK 4 and 8	XX (XX%)	XX (XX%)	(XX%, XX%)
WEEK 0, 4 and 8	XX (XX%)	XX (XX%)	(XX%, XX%)

[1] The denominator for the percentage of successful injections is the number of attempted injections.  
 Note: If a subject has more than one attempt to self-administer study treatment at a single visit, only the first attempt is included in this summary.

userid: /arenv/arprod/compound/study/final/drivers/drivername.sas DDMMYYYY HH:MM

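### Both composite success rates leave out subjects who failed one dose and did not attempt another, although their composite outcome is already a known failure; add one supplementary row per composite.

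*SAP*

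**What the plan says.** Protocol 9.4.1 and SAP 7.2 define the composite rates in the same way. For Weeks 4 and 8 the denominator is "the number of subjects attempting an injection at both Week 4 and Week 8". For all three doses the protocol says "The denominator for the percentage calculation will be the number of subjects attempting all 3 doses at Week 0, 4 and 8", and the SAP repeats the rule: "The denominator for the percentage calculation will be the number of subjects attempting all three doses at Week 0, 4 and 8". Shell TAB_INJ1 in SAP Appendix 9 applies one footnote to every row, the composite rows included: "The denominator for the percentage of successful injections is the number of attempted injections".

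Protocol 5.5 makes a failure with no later attempt possible: "subjects who permanently withdraw from study treatment will also be withdrawn from the study". It does not make it inevitable. A failed injection is not among the stopping criteria in Protocol 5.5.1, and for the home dose Protocol 6.8.2 tells subjects with concerns: "They will have the option of returning to the clinical site for further training or assistance with self-administration".

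SAP 5.3, 7.1 and 14.5.2 plan no imputation in general. Their one exception is a sensitivity analysis, named for the primary endpoint, that counts a missing or not-attempted injection as a failure when the subject withdrew because of autoinjector issues.

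In the Protocol 7.1 schedule, the row "Assessment of injection success" is marked at Visits 2 and 4 only. Its Visit 4 footnote reads "Includes both the injection outside the clinic from Week 4 and the injection in clinic at Week 8".

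**The concern.** Composite success needs every dose in the set to succeed, so one failed attempt settles the outcome. The attempters-only rule treats that settled failure as unknown when another dose in the set was not attempted. A composite success can never be lost this way, because it requires all doses to have been attempted. In any given data set the planned rate is therefore equal to, or higher than, the rate with known failures counted.

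The study's stated aim is repeat self-administration, and the composites are the only planned rates that measure success across doses within a subject. What is at stake is a possibly overstated repeat-use rate in each label group. No decision rule depends on it.

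The two composites differ in whom they omit. For Weeks 0, 4 and 8, it is anyone with a failed dose and any other dose not attempted. For Weeks 4 and 8, it is anyone who failed one of those two doses and did not attempt the other; a Week 0 failure alone does not settle that composite.

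**Working it through.** **Inputs from the documents.** Group sizes are 100 and 50 completed subjects (Protocol 9.2.2). Enrolment is 158 with dropout of up to 5% (Protocol 9.2.1). Intervals are exact Clopper-Pearson 95% (SAP 7.1).

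**The plan's own figures.** 150/0.95 = 157.9, which gives the stated 158. All 22 intervals in Protocol 9.2.2 reproduce to the whole percent. For example, 92/100 gives 84.84 to 96.48 (stated 85, 96) and 46/50 gives 80.77 to 97.78 (stated 81, 98).

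**Value of each omitted failure.** Let x be composite successes, n the subjects attempting every dose, and k the known failures left out. The planned rate is x/n; with known failures counted it is x/(n+k). The documents do not give k, and 92% is an illustrative observed rate.

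| k | Pictogram label | Standard label |
|---|---|---|
| 0 | 92/100 = 92.0% (84.8 to 96.5) | 46/50 = 92.0% (80.8 to 97.8) |
| 1 | 92/101 = 91.1% (83.8 to 95.8) | 46/51 = 90.2% (78.6 to 96.7) |
| 2 | 92/102 = 90.2% | 46/52 = 88.5% |
| 3 | 92/103 = 89.3% | 46/53 = 86.8% |

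The first omitted failure costs 0.9 points at N=100 and 1.8 points at N=50.

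**Expected k under random dropout.** Assume a true three-dose rate of 92%, equal and independent doses, and all dropout after Week 4 and before Week 8. Per-dose success is p = 0.92^(1/3) = 0.9726. The chance of a failure at Week 0 or 4 is e = 1 − p² = 0.0541. Splitting 158 in the ratio 100:50 gives about 105 and 53.

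- Pictogram: 105 × 0.05 × 0.0541 = 0.28
- Standard label: 53 × 0.05 × 0.0541 = 0.14
- Whole study: about 0.4 subjects

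The 5% is a ceiling through Week 12, so fewer would be expected before Week 8.

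**Bias when failing prompts leaving.** Let a fraction f of early failures leave, with total dropout held at 5%. The others then leave at d = (0.05 − f·e)/(1 − e).

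- Attempters-only rate = p³(1−d) / [p²(1−d) + e(1−f)]
- Rate with known failures counted = p³(1−d) / [p²(1−d) + e]

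For the two-dose composite, e = 1 − p = 0.0274, and p³ and p² are replaced by p² and p. If the true three-dose rate is 96%, p = 0.9865. Each cell gives attempters-only / known failures counted, in percent.

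| f | Three-dose, true 92.00 | Two-dose, true 94.59 | Three-dose, true 96.00 |
|---|---|---|---|
| 0.05 (random) | 92.00 / 91.74 | 94.59 / 94.46 | 96.00 / 95.86 |
| 0.30 | 93.38 / 91.82 | 95.29 / 94.48 | 96.70 / 95.88 |
| 0.80 | 96.15 / 91.96 | 96.70 / 94.52 | 98.09 / 95.92 |

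At f = 0.80 in the first column, prior failures make up 0.80 × 0.0541/0.05, about 87% of all dropouts. Nothing in the documents supports so extreme a pattern.

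**The case against.** **Random dropout.** If dropout is unrelated to success, the planned rate is unbiased, and the supplementary row is slightly low (91.74% against 92.00%) because it keeps failures with a missing dose while dropping undetermined subjects. This stands. It is why the planned rate should stay, with the new row beside it.

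**The sensitivity analysis may carry over.** SAP 7.2 opens by saying its endpoints are summarised in the same way as the primary, and SAP 7.1 contains the sensitivity analysis. That reading is arguable. However, SAP 5.3, 7.1 and 14.5.2 each name only the primary, and Appendix 8 lists no such display for the composites. Even if carried over, it would miss a failure followed by withdrawal for another recorded reason.

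**Hidden failures.** A reader might infer that the failures disappear from the report. They do not. A failed dose appears in its own single-visit row of TAB_INJ1 and in TAB_INJ2. TAB_INJ1 also prints how many subjects attempted each composite, and Listing 16 gives results by dose. Only the composite rates leave these subjects out.

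**No rule for the home dose.** A reader might infer from the schedule that a home dose before withdrawal cannot be classified. Protocol 4.1 and SAP 2.3 already assess every home dose from the completed checklist and the returned device, and Protocol 7.1 footnotes n and o provide for return and inspection at Early Withdrawal. What remains is narrow. SAP 14.3.2 re-assigns Early Withdrawal data to the next scheduled visit, which read literally would be Week 8. LIST_INJ1 points the other way, since it labels the home injection Week 4 with its own assessment date.

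**The primary endpoint.** A reader might extend the point to the Week 8 primary. That does not follow: an earlier failure does not determine a Week 8 result that was never attempted, and the primary already has its own sensitivity analysis.

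**Conclusion.** The point holds as a minor one. Both composite denominators exclude some determined failures, and the exclusion can only leave the rate unchanged or raise it. No material overstatement is shown: the number affected is unknown and may be zero, and the larger gaps in the bias table need most early failures to leave, in a design that offers retraining and does not list failure as a stopping criterion. The expected count and the bias figures rest on assumed success rates, equal independent doses and 5% dropout. The composites are Other endpoints (Protocol 3, SAP 2.2) and no hypothesis is tested, so no wrong decision follows. The reason to act is that specifying the row in advance avoids a choice after the fact if even one such subject occurs.

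**What to change.** Keep the protocol's attempters-only composite rates. In SAP 7.2, TAB_INJ1 and Tables 7.1 to 7.4, add one supplementary row per composite:

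- Failure: any dose in the set attempted and unsuccessful, whether or not the other doses were attempted (first attempt in Tables 7.1 and 7.2, best attempt in 7.3 and 7.4).
- Success: all doses in the set successful.
- Undetermined: everyone else, with the number printed.
- Denominator: successes plus failures, with an exact 95% interval.

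Add a note that the row is about 0.3 points conservative for the three-dose composite under 5% random dropout at an assumed 92% rate. Record the addition in SAP 2.1, which now says there are no other changes. Add one line to SAP 14.3.2 stating that a home dose inspected at Early Withdrawal is reported under Week 4 and is not re-assigned to the next scheduled visit.

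The cost is this SAP wording and two rows in each of four tables. No new data are collected. The downside is the small conservatism, which the note discloses.

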## 8. PHARMACOKINETIC ANALYSES

- The PK analyses will be based on the “PK” population.
- Linear and semi-logarithmic individual mepolizumab plasma concentration-time profiles will be produced for each subject. Time will be relative to the first dose of study treatment. Individual mepolizumab plasma concentration-time profile plots grouped by baseline mepolizumab use and by baseline mepolizumab use and injection site (performed only for the subset of subjects using the same injection site throughout the study) will also be produced.
- Mepolizumab plasma concentrations will be listed and summarised by nominal time and by nominal time and baseline mepolizumab use. Mean ( $\pm$ SD) and median profiles by nominal time and baseline mepolizumab use will be plotted.
- Summaries of mepolizumab plasma concentration-time data will also be produced by baseline mepolizumab use and injection site, and mean ( $\pm$ SD) and median concentration-time profiles by baseline mepolizumab use and injection site will be plotted. These summaries will be performed only for the subset of subjects using the same injection site throughout the study.
- Refer to [Appendix 3: Data Handling Conventions](#), Section [14.3.2 Reporting Process & Standards](#).

Full details of the data displays to be presented are given in [Appendix 8: List of Data Displays](#).

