## 3. OBJECTIVE(S) AND ENDPOINT(S)

The aim of this study is to assess the correct real-world use of the mepolizumab liquid drug product in autoinjector for the repeat self-administration of mepolizumab subcutaneously by determining the proportion of subjects with severe eosinophilic asthma who are successfully able to self-administer a dose of mepolizumab. For the purposes of this study, 'self-administration' is defined as either the administration of mepolizumab liquid drug product in autoinjector by the subject themselves or by their caregiver.

The objectives and endpoints associated with these objectives are outlined below:

Objectives	Endpoints
Primary	
• To assess the use of the combination product, mepolizumab liquid drug product in autoinjector for the subcutaneous self-administration of mepolizumab by subjects with severe eosinophilic asthma	• Proportion of subjects successfully able to self-administer their observed third dose at Week 8
Secondary	
• To assess the use of mepolizumab liquid drug product in autoinjector outside the clinic setting	• Proportion of subjects successfully able to self-administer their unobserved second dose outside the clinic setting at Week 4

	Objectives		Endpoints
Ot	ner		
•	To assess the use of mepolizumab liquid drug product in autoinjector both inside and outside of the clinic setting	•	Proportion of subjects successfully able to self-administer their observed first dose at Week 0
		•	Proportion of subjects successfully able to self-administer both their unobserved second dose and observed third dose at Weeks 4 and 8
		•	Proportion of subjects successfully able to self-administer all three doses at Weeks 0, 4 and 8
•	To evaluate autoinjector use & functionality	•	Device usability/functionality questionnaire completed at the End of Study/Early Withdrawal Visit
•	To evaluate any autoinjector injection errors/failures related to use or device performance	•	Evaluation of user/device errors Root cause analysis of each unsuccessful injection
•	To characterise the subject experience of using the mepolizumab liquid drug product in autoinjector	•	Subject Exit Interviews completed over the telephone after the End of Study/Early Withdrawal Visit
•	To assess mepolizumab plasma trough concentrations following the SC administration of mepolizumab liquid drug product in autoinjector	•	Mepolizumab plasma trough concentrations (Ctrough) at Weeks 4, 8 and 12

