- c. Parasitic screening is only required in countries with high-risk or for subjects who have visited high-risk countries in the past 6 months. Sites should use local laboratories.
- d. Perform prior to mepolizumab administration during the study and prior to restarting pre-study mepolizumab treatment on study completion/early withdrawal.
- e. Subjects will be instructed to contact clinical study staff at any time if they have concerns or questions regarding self-administration. They will have the option of returning to the clinical site for further training or assistance with self-administration. Requirement for additional training or assistance will be documented.
- f. Self-administration of mepolizumab using the autoinjector should occur within 24 hours following the clinic visit.
- g. Includes measurement of eosinophil levels for pharmacodynamic analysis at Visits 2, 3, 4 and 5
- h. Pharmacogenetic sample may be drawn any time after the respective informed consent form is signed and the subject is enrolled.
- i. Vital signs include temperature, sitting blood pressure, respiratory rate and pulse.
- j. Any SAEs assessed as related to study participation (e.g., study treatment, protocol-mandated procedures, invasive tests, or change in existing therapy) or related to a GSK concomitant medication, will be recorded from the time a subject consents to participate in the study up to and including any follow up contact. All other AEs/SAEs are recorded from the start of study treatment until the End of Study / Early Withdrawal visit.
- k. Injection site reactions (e.g., induration, erythema, edema, rash, pruritus, pain) are to be recorded on both AE and SAE CRF forms.
- I. Information on systemic reactions and events that meet the anaphylaxis criteria is collected on both AE and SAECRF forms
- m. Patient diary should be dispensed prior to administration of injection
- n. For any subject who withdraws prior to Week 12, patient diary and study drug for self-administration outside of clinic will be returned at the Early Withdrawal visit (if applicable).

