# 7.10. Pharmacokinetics

Blood samples for analysis of mepolizumab plasma concentration will be obtained as per the Time and Events table (Section 7.1). Samples obtained at Visits 2, 3, 4 and 5 should be drawn prior to dosing. The date and exact time of collection for each sample will be documented in the eCRF.

Details for collection and processing of samples may be found in the SRM.

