## 9.4.4. Pharmacokinetic Analyses

Pharmacokinetic analysis will be the responsibility of the Clinical Pharmacology Modeling & Simulation department within GSK.

PK concentrations will be presented in graphical and/or tabular form and will be summarized descriptively overall, by previous mepolizumab use (i.e. not receiving mepolizumab treatment at Visit 1 or receiving 100 mg SC mepolizumab administered for the treatment of severe eosinophilic asthma every 4 weeks for at least 12 weeks prior to Visit 1) and by injection site.

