## 2. SUMMARY OF KEY PROTOCOL INFORMATION

### 2.1. Changes to the Protocol Defined Statistical Analysis Plan

An additional analysis population was defined for reporting screen failures and inclusion/exclusion criteria deviations. This population is described in Section [4](#).

There are no other changes to the protocol defined statistical analysis plan.

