## 9. BLOOD EOSINOPHILS

- Blood eosinophil analyses will be based on the “Pharmacodynamic” population.
- Blood eosinophil values will be  $\log_e$ -transformed prior to summarising. Non-detectable values of 0 GI/L, will be replaced by half of the lowest observed detectable (non-zero) value in the study data set, prior to log transformation.
- Blood eosinophil values will be summarised by visit, and by visit and baseline mepolizumab use.
- Blood eosinophil values will also be summarised by visit, baseline mepolizumab use and injection site. These summaries will be performed only for the subset of subjects using the same injection site throughout the study.
- Absolute and ratio to baseline blood eosinophils will be listed.

Full details of data displays to be presented are given in [Appendix 8](#): List of Data Displays.

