8.8	PK	-	Scatter Plot of Individual Plasma Mepolizumab Concentration-Time Data by Week 12 Binding Antibody Result	Use grey open circles for data points for subjects with negative binding antibody. Use larger filled blue circles for data points for subjects with positive binding antibody, and annotate data points with subject number.	SAC
Pharmacokinetic – Tables					
8.1	PK	PK01	Summary of Plasma Mepolizumab Concentration-Time Data		SAC
8.2	PK	PK01	Summary of Plasma Mepolizumab Concentration-Time Data by Baseline Mepolizumab Use		SAC
8.3	PK	PK01	Summary of Plasma Mepolizumab Concentration-Time Data by Baseline Mepolizumab Use and Injection Site – Subjects Using the Same Injection Site Throughout the Study	Include only the subset of subjects using the same injection site for all doses of study treatment.	SAC

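### By-site PK and eosinophil tables drop subjects at Weeks 4 and 8 for site choices at later doses, which cannot affect those values

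*SAP*

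**What the plan says.** Protocol 9.4.3 and 9.4.4 plan summaries of eosinophil ratio to baseline and of PK concentrations overall, by previous mepolizumab use "and by injection site". They do not say how to classify a subject who changes site.

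The SAP supplies a rule. On PK by baseline use and site, SAP 8 says: "These summaries will be performed only for the subset of subjects using the same injection site throughout the study". SAP 9 says: "Blood eosinophil values will also be summarised by visit, baseline mepolizumab use and injection site", and adds the same restriction. The programming notes in SAP Appendix 8 make it operational: "Include only the subset of subjects using the same injection site for all doses of study treatment". The note covers PK Table 8.3 and Figures 8.3, 8.6 and 8.7, and PD Tables 9.5 and 9.6 and Figures 9.2 and 9.4. There is no visit-specific version and no rationale.

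On timing, the protocol's PK endpoint (Section 3) is "Mepolizumab plasma trough concentrations (Ctrough) at Weeks 4, 8 and 12", and the eosinophil ratio uses the same weeks. Protocol 7.10 says: "Samples obtained at Visits 2, 3, 4 and 5 should be drawn prior to dosing". In the Time and Events Table (Protocol 7.1), footnote d marks both PK and haematology at Visits 2 to 5: "Perform prior to mepolizumab administration during the study and prior to restarting pre-study mepolizumab treatment on study completion/early withdrawal". Footnote f places the home dose in the 24 hours after Visit 3.

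SAP 2.1 describes one added analysis population and then says: "There are no other changes to the protocol defined statistical analysis plan".

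**The concern.** A same-site rule is reasonable where several doses contribute to the measured value. Here a single subset, defined over all three doses, is applied to samples taken after only one or two of them. Inclusion at Week 4 then depends on what the subject does later, and usable values leave the by-site display for a reason unrelated to their content.

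The by-site tables are already finely divided: three sites (SAP 5.4.3) by two levels of baseline mepolizumab use make six cells. Upper arm is open only to caregivers, so that cell may be thin from the start. What is at stake is the precision of a descriptive summary. The primary and secondary endpoints are untouched.

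**Working it through.** **Timing.** Setting the dosing and sampling schedule against the rule gives:

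| Sample | Study doses already given | Doses whose site decides inclusion under the SAP | Doses that cannot affect the value but still decide inclusion |
|---|---|---|---|
| Week 4 (Visit 3, pre-dose) | 1 | 1, 2, 3 | 2, 3 |
| Week 8 (Visit 4, pre-dose) | 1, 2 | 1, 2, 3 | 3 |
| Week 12 (Visit 5) | 1, 2, 3 | 1, 2, 3 | none |

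The rule fits Week 12 and is too strict at Weeks 4 and 8.

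**Size.** The plan states no figure to reproduce and no rate of site switching, so the rates below are assumptions. Let w be the probability of a change of site at each of doses 2 and 3, independently.

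- Same site for all three doses: (1 − w)².
- Same site for doses 1 and 2: 1 − w.
- Eligible at Week 4 on the dose 1 site: everyone with a sample.

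The counts use 158, the planned enrolment in Protocol 9.2.1, and ignore dropout. With a constant standard deviation on the log scale, interval width varies as 1/√n. The ratio of the width using all eligible subjects to the width under the SAP rule is therefore √((1 − w)²) = 1 − w at Week 4, and √((1 − w)²/(1 − w)) = √(1 − w) at Week 8.

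| w (assumed) | SAP subset, every visit | Eligible at Week 8 | Eligible at Week 4 | Width ratio, Week 8 | Width ratio, Week 4 |
|---|---|---|---|---|---|
| 10% | 81%, 128 | 142 | 158 | 0.95 | 0.90 |
| 20% | 64%, 101 | 126 | 158 | 0.89 | 0.80 |
| 30% | 49%, 77 | 111 | 158 | 0.84 | 0.70 |
| 50% | 25%, 40 | 79 | 158 | 0.71 | 0.50 |

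The counts are totals before division into six cells. The width ratios bear directly on eosinophils, whose shells show geometric means with 95% confidence intervals. For PK, SAP 8 specifies means with SD and medians for the profiles, so there the ratios describe precision and not a planned interval.

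**Prior users.** For subjects not on mepolizumab at Visit 1, the first dose is the only current exposure behind the Week 4 value. Prior users had at least 12 weeks of dosing every 4 weeks before Visit 1, so pre-study doses contribute too. The documents give no half-life. Assume first-order decline, equal doses every 28 days, four pre-study doses and a half-life T, and let r = 2^(−28/T). The share of the Week 4 trough from pre-study doses is (r + r² + r³ + r⁴)/(1 + r + r² + r³ + r⁴):

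- T = 14 days: r = 0.25, share about 25%.
- T = 21 days: r = 0.40, share about 39%.
- T = 28 days: r = 0.50, share about 48%.

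The site comparison is thus cleanest in subjects not on mepolizumab at Visit 1. The same-site rule does not remove the carry-over in the others, because it looks only at study doses.

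**The case against.** The strongest defence is that a fixed cohort is a legitimate choice. Most of the affected displays are profiles over time, and with constant membership a change between visits cannot come from a change in who is counted. That stands for the figures. It is weaker for tables read visit by visit, whose eosinophil shells already print n for each visit.

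Several stronger readings are tempting, and the documents do not support them:

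- **That the data are thrown away.** They leave only the by-site displays. They remain in the overall and baseline-use summaries and in Listings 20 and 41. Figure 8.1 plots every PK subject with the site of each dose marked.
- **That these tables are the trial's only check on site dependence.** Figure 8.1 and the listing of exposure data also show site. No stated objective concerns site dependence, and Protocol 2.1 assigns exposure comparability to a separate study. Site is not randomised, so any contrast is confounded under either rule.
- **That the Week 4 site means are biased.** Inclusion does depend on later behaviour, but nothing in the documents links a later choice of site to the Week 4 value. The supported complaint is lost precision and an avoidable condition on the future.
- **That SAP 2.1 conceals a change.** The protocol leaves analysis detail to the reporting and analysis plan, and some rule for mixed-site subjects was needed. The restriction does narrow the protocol's wording and deserves a line there, but this is minor.
- **That the subset favours early withdrawals.** Read literally, a subject with one dose has used one site throughout, but the SAP does not say how such subjects are handled. Planned dropout is at most 5%, about 8 of 158.

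One practical objection also stands. The dose 1 site is not always clear: the SAP allows for repeat attempts at a visit, its injection-success listing shell shows a failed Week 0 injection followed by an unscheduled one, and its injection-site table has a category for other sites or intervention. A grouping by dose 1 site needs a rule for these subjects.

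**Conclusion.** The point holds as a cheap improvement of low importance. The by-site rule excludes subjects at Week 4 for the sites of doses 2 or 3, and at Week 8 for the site of dose 3, when those doses come after the sample. This follows from the documents' own timing and needs no assumption.

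The size of the loss is unknown. Under assumed switching of 10% to 50% at each later dose, Week 4 intervals on all eligible subjects would be 10% to 50% narrower, and Week 8 intervals about 5% to 29% narrower. Those ranges rest on independent switching, no dropout and equal variance. If nearly everyone keeps one site, the change makes almost no difference, and thin upper-arm cells may stay thin in any case. The endpoints are descriptive and listed as 'other', so no primary, secondary or safety conclusion depends on this.

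**What to change.** In Tables 8.3, 9.5 and 9.6, define the site group at each visit from the study doses given before that sample, still split by baseline mepolizumab use:

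- Week 4: site of dose 1, all PK or PD population subjects with a value.
- Week 8: subjects with doses 1 and 2 at the same site.
- Week 12: subjects with doses 1 to 3 at the same site.

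Exclude or footnote subjects whose dose 1 site was 'Other' or who had repeat attempts at different sites. Keep the fixed same-site cohort for the profile figures (8.3, 8.6, 8.7, 9.2 and 9.4) and label it as such. Note the by-site restriction in SAP 2.1.

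The site of every dose is already recorded (Protocol 6.8.1 and 6.8.2), so the cost is SAP wording and programming notes. The downside is that n will differ between visits and between tables and figures; a footnote should say so.
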